### **9.7 Mini-Mental State Examination**

The mean changes from baseline to Week 12/ET visit in the double-blind treatment period in MMSE will be tabulated and analyzed by treatment group using ANCOVA. The ANCOVA model will include the baseline item score as covariate and treatment group as main effect. The analyses will be performed for Safety Sample.

### **9.8 Suicidality Data**

The mean changes from baseline to Week 12/ET visit in the double-blind treatment period in Sheehan-STS individual item scores, suicidal ideation subscale score, suicidal behavior subscale score, or total score will be tabulated and analyzed by treatment group using ANCOVA. The ANCOVA model will include the baseline item score as covariate and treatment group as main effects.

Incidence of treatment emergent suicidal ideation, suicidal behavior will be summarized by treatment, and overall.

### **9.9 Concomitant Medications**

Number and proportion of subjects taking concomitant medications prior to IMP, during the double-blind treatment period, and after IMP are tabulated by drug classification using the World Health Organization drug dictionary.

### **9.10 Extent of Exposure**

The start date of double-blind IMP with brexpiprazole or placebo will be the first day of double-blind dosing. The number and percentage of subjects who receive double-blind IMP will be presented by week and by treatment group. Each dosing week will be based on the actual week; i.e., Day 1 to 7 in Week 1, Day 8 to 14 in Week 2, etc. This summary will be performed on the Safety Sample.

The number and percentage of completers will be presented by week and by treatment group.

The mean daily dosage will be summarized by week and treatment group using descriptive statistics. The mean daily dosage per subject per week will be determined for each week of the trial. This will be calculated by dividing the sum of individual total doses by the number of days in the week interval. The summary will contain for each

treatment group the number of subjects receiving double-blind IMP, and the mean and range of the mean daily dose for each week.

## 10 Conventions

### 10.1 Trial Visit Windows

Trial visit windows will be used to map visits using trial day intervals. This visit window convention applies to tables and listings for all efficacy and safety scales. This derived trial window variable will be named as WEEK and will be footnoted. In listings it will be listed along with the case report form (CRF) trial visit.

### 10.2 Pooling of small centers

Primary efficacy analysis will be performed on the ITT Efficacy Sample which comprises those subjects in the randomized sample who have a baseline value and at least one post-randomization value for CMAI total score in the double-blind treatment period.

Small centers will be defined as centers that do not have at least one evaluable subject (evaluable with regard to the primary efficacy variable) in each treatment arm in the double-blind treatment period. All small centers will be pooled to form “pseudo centers” for the purpose of analysis according to the following algorithm. Small centers will be ordered from the largest to the smallest based on the number of evaluable subjects (ie, subjects who have a baseline value and at least one post-randomization value for CMAI total score in the double-blind treatment period). The process will start by pooling the largest of the small centers with the smallest of the small centers until a non-small center is formed. This process will be repeated using the centers left out of the previous pass. In case of ties in center size, the center with the smallest center code will be selected. If any centers are left out at the end of this process, they will be pooled with the smallest pseudo centers, or if no pseudo centers exist, they will be pooled with the smallest non-small center. The pooling of the small centers will be performed within each region (North America and Other).

### 10.3 Scales: Rules for Scoring and Handling of Missing Data

#### 10.3.1 Cohen-Mansfield Agitation Inventory

The CMAI consists of 29 items all rated on a 1 to 7 scale with 1 being the “best” rating and 7 being the “worst” rating. The CMAI total score is the sum of ratings for all 29 items. The possible total scores are from 29 to 203. The CMAI total score will be unevaluable if less than 24 of the 29 items are recorded. If 24 to 28 of the 29 items are recorded, the total score will be the mean of the recorded items multiplied by 29 and then rounded to the first decimal place.

**Factor 1:** Aggressive behavior: Hitting (including self), kicking, scratching, grabbing onto people, pushing, hurt self or other (cigarette, hot water, etc.), throwing things, cursing or verbal aggression, spitting (include at meals), tearing things or destroying property, screaming, biting.

Criteria for agitated status based on Factor 1:

- at least one aggressive behavior occurring at a frequency of at least 4; or
- at least two aggressive behavior occurring at a frequency of at least 3; or
- at least three aggressive behavior occurring at a frequency of at least 2;

**Factor 2:** Physically nonaggressive behavior: Pace, aimless wandering, trying to get to a different place, general restlessness, inappropriate dress or disrobing, handling things inappropriately, performing repetitious mannerisms.

Criteria for agitated status based on Factor 2:

- at least one physically nonaggressive behavior occurring at a frequency of at least 5; or

- at least two physically nonaggressive behavior occurring at a frequency of at least 4; or
- at least three physically nonaggressive behavior occurring at a frequency of at least 3; or
- at least four physically nonaggressive behavior occurring at a frequency of at least 2;

**Factor 3:** Verbally agitated behavior: Complaining, constant unwarranted request for attention or help, repetitious sentences or questions, negativism.

Criteria for agitated status based on Factor 3:

- at least one verbally agitated behavior occurring at a frequency of at least 5; or
- at least two verbally agitated behavior occurring at a frequency of at least 4; or
- at least three verbally agitated behavior occurring at a frequency of at least 3; or
- at least four verbally agitated behavior occurring at a frequency of at least 2;

**Factor 4:** Hiding things, hoarding things.

The following items are not included in factors derivation: Intentional Falling; Making Verbal Sexual Advances; Making Physical Sexual Advances; Strange Noises (weird laughter or crying); Eating or Drinking Inappropriate Substances.

### 10.3.2 Clinical Global Impression-Severity of Illness Scale

[figure not shown]
The severity of agitation for each subject will be rated using the Clinical Global Impression-Severity of Illness Scale (CGI-S). To perform this assessment, the investigator (or designee) will answer the following question: "Considering your total clinical experience with this particular population, how mentally ill (as related to agitation) is the subject at this time?" Response choices are 0 = not assessed; 1 = normal, not at all ill; 2 = borderline mentally ill; 3 = mildly ill; 4 = moderately ill; 5 = markedly ill; 6 = severely ill; and 7 = among the most extremely ill subjects. The score 0 (not assessed) will be set to missing. The CGI-S is therefore a 7-point scale from 1 through 7.

### 10.3.3 Clinical Global Impression-Improvement Scale

The efficacy of brexpiprazole in the treatment of agitation will be rated for each subject using the CGI-I. The investigator (or designee) will rate the subject's total improvement (as related to agitation) whether or not it is due entirely to IMP. Response choices are 0 = not assessed, 1 = very much improved, 2 = much improved, 3 = minimally improved, 4 = no change, 5 = minimally worse, 6 = much worse, and 7 = very much worse.

This is also a 7-point scale (1 to 7), with 1 being very much improved and 7 being very much worse. The scale also includes 0: not assessed, which will be set to missing for

purposes of analysis. At each visit other than randomization, the global improvement will be judged with respect to subject's condition at randomization.

### 10.3.5 Hachinski Ischemic Scale (Rosen Modification)

The Rosen-modified Hachinski Ischemic Scale assesses whether a subject's dementia is likely due to vascular causes by the response to 8 questions: abrupt onset, stepwise deterioration, somatic complaints, emotional incontinence, history of hypertension, history of stroke, focal neurologic signs, and focal neurologic symptoms. The Rosen modified Hachinski Ischemic Scale will be completed to assess eligibility for the trial by the same neurologist who performs the neurological examination.

### 10.3.6 Simpson-Angus Scale

The Simpson-Angus Scale is a rating scale used to measure EPS. The Simpson-Angus Scale is a 10-item scale, with each item rated from 0 to 4, with 0 being normal and 4 being the worst. The Simpson-Angus Scale total score is the sum of ratings for all 10 items, with possible total scores from 0 to 40. The Simpson-Angus Scale total score

will be un-evaluable if less than 8 of the 10 items are recorded. If 8 or 9 of the 10 items are recorded, the total score will be the mean of the recorded items multiplied by 10 and then rounded to the first decimal place.

### **10.3.7 Abnormal Involuntary Movement Scale**

The AIMS is a 12-item scale. The first 10 items are rated from 0 to 4 (0 = best, 4 = worst). An item score of 0, depending on the item, either means: no abnormal involuntary movement (AIM), or no incapacitation due to AIM, or no awareness of AIM. An item score of 4 either means: severe AIM, or severe incapacitation due to AIM, or being aware of, and severe distress caused by AIM. Items 11 and 12, related to dental status, have dichotomous responses, 0 = no and 1 = yes. The AIMS total score is the sum of the ratings for the first seven items. The possible total scores are from 0 to 28. The AIMS total score will be un-evaluable if less than 6 of the first 7 items are recorded. If 6 of the items are recorded, then the total score will be the mean of the recorded items multiplied by 7 and then rounded to the first decimal place.

### **10.3.8 Barnes Akathisia Rating Scale**

BARS will be used to assess the presence and severity of akathisia. This scale consists of 4 items. Only the 4th item, the Global Clinical Assessment of Akathisia, will be evaluated in this trial. This item is rated on a 6-point scale, with 0 being best (absent) and 5 being worst (severe akathisia).

### **10.3.9 Sheehan Suicidality Tracking Scale**

Suicidality will be monitored during the trial using the Sheehan-STS. The Sheehan-STS is a prospective scale that assesses treatment-emergent suicidal thoughts and behaviors. Each item of the Sheehan-STS is scored on a 5-point Likert scale (0 = not at all; 1 = a little; 2 = moderate; 3 = very; and 4 = extremely). The Sheehan-STS can be analyzed as individual item scores, suicidal ideation subscale score, suicidal behavior subscale score, or total score. The trial will use the “Screening” and “Since Last Visit” version of the scale. The “Screening” Sheehan-STS form will be completed at the screening visit to determine eligibility. Any subject with evidence of serious risk of suicide based on the Sheehan-STS, ie, a score of 3 or 4 on any one question 2 through 6 or 11 or a score of 2 or higher on any one questions 1a, 7 through 10, or 12, or who, in the opinion of the investigator, present a serious risk of suicide should be excluded from the trial. The “Since Last Visit” Sheehan-STS form will be completed at all other visits. The medical monitor should be contacted if a score of 3 or 4 on any one question 3 through 6 or 11 or a score of 2 or higher on any one questions 1a, 7 through 10, or 12, or 18, or if suicide results in death.

### 10.3.10 Mini-Mental State Examination

The MMSE is a brief practical test for assessing cognitive dysfunction. The test consists of 5 sections (orientation, registration, attention and calculation, recall, and language) and has a total possible score of 30. The MMSE is used for screening subjects and is also to be completed at Week 12/ET.

The MMSE is a 19-item scale. Items 1 to 10, 15, and 17 to 19 are rated on a scale from 0 to 1, item 14 is rated on a 0 to 2 scale, items 11, 13 and 16 are rated on a scale from 0 to 3, and Item 12 is rated on a scale from 0 to 5. Low scores are the worst, high scores are the best. The MMSE total score is calculated by adding the individual item scores.

The possible range for the MMSE total score is from 0 to 30. If the maximum total of the missing items could contribute more than 6 points to the total score then the total score will be set to missing. Otherwise a mean non-missing items score will be calculated by summing the non-missing items and dividing them by the maximum score possible from the non-missing items. For missing items with possible scores from 0 to 1, the mean score will be imputed for each missing item. If item 14 is missing, two times this mean will be imputed for item 14. If items 11, 13, or 16 are missing three times this mean for will be imputed each missing item. If item 12 is missing 5 times then this mean will be imputed for item 12. After all by-item imputation has been done, the individual item scores will be added and this sum will be rounded to the first decimal place to arrive at an imputed total score. In other terms, the MMSE total score is simply the mean non-missing items score multiplied by 30, and then rounded to the first decimal place.

**Appendix 1****Criteria for Identifying Laboratory Values of Potential Clinical Relevance**

Laboratory Tests	Criteria
Chemistry	
AST (SGOT)	$\geq 3 \times$ ULN
ALT (SGPT)	$\geq 3 \times$ ULN
Alkaline phosphatase	$\geq 3 \times$ ULN
LDH	$\geq 3 \times$ ULN
BUN	$\geq 30$ mg/dL
Creatinine	$\geq 2.0$ mg/dL
Uric Acid	
Men	$\geq 10.5$ mg/dL
Women	$\geq 8.5$ mg/dL
Bilirubin (total)	$\geq 2.0$ mg/dL
CPK	$\geq 3 \times$ ULN
Prolactin	$>$ ULN
Hematology	
Hematocrit	
Men	$\leq 37\%$ and decrease of $\geq 3$ percentage points from Baseline
Women	$\leq 32\%$ and decrease of $\geq 3$ percentage points from Baseline
Hemoglobin	
Men	$\leq 11.5$ g/dL
Women	$\leq 9.5$ g/dL
White blood count	$\leq 2,800/\text{mm}^3$ or $\geq 16,000/\text{mm}^3$
Eosinophils	$\geq 10\%$
Neutrophils	$\leq 15\%$
Absolute neutrophil count	$\leq 1,000/\text{mm}^3$
Platelet count	$\leq 75,000/\text{mm}^3$ or $\geq 700,000/\text{mm}^3$
Urinalysis	
Protein	Increase of $\geq 2$ units
Glucose	Increase of $\geq 2$ units
Casts	Increase of $\geq 2$ units
Additional Criteria	
Chloride	$\leq 90$ mEq/L or $\geq 118$ mEq/L
Potassium	$\leq 2.5$ mEq/L or $\geq 6.5$ mEq/L
Sodium	$\leq 126$ mEq/L or $\geq 156$ mEq/L
Calcium	$\leq 8.2$ mg/dL or $\geq 12$ mg/dL
Glucose	
Fasting	$\geq 100$ mg/dL
Non-Fasting	$\geq 200$ mg/dL
Total Cholesterol, Fasting	$\geq 240$ mg/dL
LDL Cholesterol, Fasting	$\geq 160$ mg/dL
HDL Cholesterol, Fasting	
Men	$< 40$ mg/dL
Women	$< 50$ mg/dL
Triglycerides, Fasting	$\geq 150$ mg/dL

## Appendix 2      Criteria for Identifying Vital Signs of Potential Clinical Relevance

Variable	Criterion Value a	Change Relative to Baseline a
Heart Rate b	> 120 bpm	≥ 15 bpm increase
	< 50 bpm	≥ 15 bpm decrease
Systolic Blood Pressure b	> 180 mmHg	≥ 20 mmHg increase
	< 90 mmHg	≥ 20 mmHg decrease
Diastolic Blood Pressure b	> 105 mmHg	≥ 15 mmHg increase
	< 50 mmHg	≥ 15 mmHg decrease
Orthostatic Hypotension	≥ 20 mmHg decrease in systolic blood pressure and a ≥ 25 bpm increase in heart rate from supine to sitting/standing	Not Applicable (baseline status not considered)
Weight	—	≥ 7% increase ≥ 7% decrease

a In order to be identified as potentially clinically relevant, an on-treatment value must meet the “Criterion Value” and also represent a change from the subject’s baseline value of at least the magnitude shown in the “Change Relative to Baseline” column.

b As defined in "Supplementary Suggestions for Preparing an Integrated Summary of Safety Information in an Original NDA Submission and for Organizing Information in Periodic Safety Updates," FDA Division of Neuropharmacological Drug Products draft (2/27/87).

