9.	Subjects with evidence of serious risk of suicide based on the Sheehan-Suicidality Tracking Scale, ie, a score of 3 or 4 on any one question 2 through 6 or 11; or a score of 2 or higher on any one question 1a, 7 through 10, or 12; or who, in the opinion of the investigator, present a serious risk of suicide.
10.	Subjects who currently have clinically significant neurological, hepatic, renal, metabolic, hematological, immunological, cardiovascular, pulmonary, gastrointestinal, or psychiatric disorders. Clinically significant cardiovascular disorders include uncontrolled atrial fibrillation, heart failure, or ischemic heart disease. Surrogates for uncontrolled cardiovascular disease would include recent (within the last 6 months) hospitalizations or procedures, such as percutaneous coronary intervention or coronary artery bypass surgery. Medical conditions that are minor or well-controlled may be considered acceptable if the condition does not expose the subject to an undue risk of a significant adverse event or interfere with assessments of safety or efficacy during the course of the trial. The medical monitor should be contacted in any instance where the investigator is uncertain regarding the stability of a subject's medical condition(s) and the potential impact of the condition(s) on trial participation.

Table	3.4.3-1 Exclusion Criteria
11.	Subjects with uncontrolled hypertension (DBP > 95 mmHg) or symptomatic hypotension, or orthostatic hypotension, which is defined as a decrease of \geq 30 mmHg in SBP or a decrease of \geq 20 mmHg in DBP within 3 minutes of standing compared to the previous supine blood pressure, OR development of symptoms. Abnormal vital signs results should be repeated to ensure reproducibility of the abnormality before excluding a subject based on the criteria noted above.
12.	Subjects with diabetes mellitus (IDDM and non-IDDM) may be eligible for the trial if their condition is stable and well-controlled as determined by satisfying ALL of the following criteria at screening and baseline: • Screening HbA _{1c} < 8.0%, AND
	• Screening glucose must be $\leq 125 \text{ mg/dL}$ (fasting) or $< 200 \text{ mg/dL}$ (nonfasting). If the
	nonfasting screening glucose is ≥ 200 mg/dL, subjects must be retested in a fasted state
	and the retest value must be $\leq 125 \text{ mg/dL}$, AND
	Subject has not had any hospitalizations within the 3 months prior to screening due to diabetes or complications related to diabetes.

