3.7.5.3.3 Vital Signs

Vital sign measurements will include body weight, body temperature, systolic blood pressure (SBP), diastolic blood pressure (DBP), and heart rate. The following guidelines will aid in the standardization of body weight measurements:

- The same scale should be used to weigh a given subject each time, if possible.
- Scales should be calibrated and reliable; scales should be at zero just prior to each subject's weigh-in session.
- A subject should void prior to being weighed and be minimally clothed (ie, no shoes
 or heavy overgarments).
- Weight should be recorded before a subject's meal and at approximately the same time at each visit (screening, baseline, Week 12 or ET).

Blood pressure and heart rate measurements will be made in the supine, sitting, and standing positions. The supine measurements will be performed first, followed by sitting, and finally standing. Blood pressure and heart rate measurements in the supine position should be taken after the subject has been lying for at least 5 minutes. The sitting and standing measurements should be taken within 1 to 3 minutes of changing positions. Vital signs scheduled at the same visit as blood samples are to be completed before blood is drawn.

Subjects with uncontrolled hypertension (screening DBP > 95 mmHg in any position) or symptomatic hypotension at screening or baseline are excluded from the trial as are subjects with orthostatic hypotension, which is defined as a decrease of \geq 30 mmHg in SBP or a decrease of \geq 20 mmHg in DBP within 3 minutes of standing compared to the previous supine blood pressure or development of symptoms (see Table 3.7-1). In addition, subjects should be excluded if they have any other vital sign measurement at screening or baseline that, in the investigator's judgment, is medically significant in that it would impact the safety of the subject or the interpretation of the trial results. However, any abnormal screening or baseline vital sign result(s) considered to be clinically significant should be repeated to confirm the finding(s) before excluding the subject from the trial. Refer to Appendix 3 for a list of potentially clinically significant vital signs.

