Appendix 3 Criteria for Identifying Vital Signs of Potential Clinical Relevance

Variable	Criterion Value ^a	Change Relative to Baseline ^a
Heart rate ^b	> 120 bpm	≥ 15 bpm increase
neart rates	< 50 bpm > 180 mmHg	≥ 15 bpm decrease
Systolic blood pressure ^b	> 180 mmHg	≥ 20 mmHg increase
Systolic blood pressure	< 90 mmHg	≥ 20 mmHg decrease
Diagtalia bland maggarah	> 105 mmHg	≥ 15 mmHg increase
Diastolic blood pressure ^b	< 50 mmHg	≥ 15 mmHg decrease
	≥ 20 mmHg decrease in systolic blood	Not applicable
Orthostatic hypotension	pressure and a \geq 25 bpm increase in	(baseline status not
	heart rate from supine to sitting/standing	considered)
Weight	_	≥ 7% increase
weigni	_	≥ 7% decrease

bpm = beats per minute

^a In order to be identified as potentially clinically relevant, an on-treatment value must meet the "Criterion Value" and also represent a change from the subject's baseline value of at least the magnitude shown in the "Change Relative to Baseline" column.

b As defined in "Supplementary Suggestions for Preparing an Integrated Summary of Safety Information in an Original New Drug Application Submission and for Organizing Information in Periodic Safety Updates," FDA Division of Neuropharmacological Drug Products draft (2/27/87).

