### 9.3 Physical and Neurological Examination and Vital Signs

Physical and neurological examination findings will be listed by subject.

Summary statistics for change from baseline in vital signs, body weight, and waist circumference will be provided by treatment group.

In addition, the incidence of treatment-emergent PCR values identified using prospectively defined criteria in [Appendix 2](#) for vital signs and body weight will be summarized by treatment group. Listing of PCRs by subject and by test will be provided.

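### The on-treatment orthostatic hypotension flag requires a 25 bpm pulse rise and has no diastolic limb, so it misses falls that meet the trial's own exclusion definition

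*SAP*

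**What the plan says.** SAP Section 9.3 plans to summarise by treatment group "the incidence of treatment-emergent PCR values identified using prospectively defined criteria in" Appendix 2. The orthostatic hypotension row of that appendix has a systolic limb, at least a 20 "mmHg decrease in systolic blood pressure and a" pulse limb joined to it: at least a 25 "bpm increase in heart rate from supine to sitting/standing". Both must hold. The row's baseline column is marked not applicable ("baseline status not considered"). Protocol Appendix 3 carries the same rule, down to "heart rate from supine to sitting/standing".

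Exclusion criterion 11 (Protocol Section 3.4.3) defines orthostatic hypotension as a systolic fall of at least 30 mmHg or a diastolic fall of at least 20 mmHg "within 3 minutes of standing compared to the previous supine blood pressure, OR development of symptoms". Protocol Section 3.7.5.3.3 repeats this, ending "mmHg in DBP within 3 minutes of standing compared to the previous supine blood pressure or development of symptoms". Neither place sets a heart-rate condition.

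On data collection, Section 3.7.5.3.3 states: "Blood pressure and heart rate measurements will be made in the supine, sitting, and standing positions". Sitting and standing readings are due 1 to 3 minutes after the change of position. Table 3.7-1 schedules vital signs at screening, baseline and every treatment visit.

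**The concern.** One term has two meanings in the same trial. A subject can have, on treatment, a postural fall that would have barred entry, and the row named for that event stays empty. Because the pulse limb is compulsory, no pressure fall of any size sets the flag without a 25 bpm rise. Because there is no diastolic limb, an isolated diastolic fall cannot set it at all.

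Safety and tolerability are the secondary objective, subjects may be up to 90 years old, and a 3 mg/day dose is being explored above the dose range of the two completed trials in this population. Inclusion requires an MMSE score of 5 to 22, while adverse events are elicited by an open question about how the subject has felt (Protocol Section 5.2). A count based on measurements is therefore worth having, and the planned one could show few events in either arm for reasons of definition alone.

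**Working it through.** The plan states no figure to reproduce, so the check compares the two rules.

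**Inputs.** Changes are from supine; falls are positive.

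- Flag (SAP Appendix 2, Protocol Appendix 3): systolic fall ≥ 20 AND heart-rate rise ≥ 25, sitting or standing (the slash is read as either posture).
- Exclusion (Protocol Sections 3.4.3 and 3.7.5.3.3): systolic fall ≥ 30 OR diastolic fall ≥ 20 OR symptoms, within 3 minutes of standing.

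**Step 1: apply both rules to test cases without symptoms.**

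| Systolic fall (mmHg) | Diastolic fall (mmHg) | Heart-rate rise (bpm) | Flag | Exclusion |
|---|---|---|---|---|
| 30 | 0 | 10 | no | yes |
| 30 | 0 | 24 | no | yes |
| 40 | 25 | 15 | no | yes |
| 60 | 30 | 24 | no | yes |
| 10 | 20 | 30 | no | yes |
| 30 | 20 | 25 | yes | yes |
| 20 | 10 | 25 | yes | no |
| 25 | 15 | 30 | yes | no |

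The first four rows fail the flag on pulse alone. The fifth has enough pulse rise but fails on systolic fall, with no diastolic limb to catch it. The last two are flagged without meeting the exclusion rule. So neither rule contains the other, and the pulse condition is not the only cause of the gap.

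**Step 2: see whether the other PCR rows catch a missed case.** Take 140/80 mmHg with pulse 70 supine and 100/58 mmHg with pulse 85 standing, and assume sitting values lie between.

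- Systolic fall 140 − 100 = 40 ≥ 30 and diastolic fall 80 − 58 = 22 ≥ 20: both pressure limbs of criterion 11 are met.
- Heart-rate rise 85 − 70 = 15 < 25: not flagged.
- Low systolic row needs < 90 mmHg; the lowest value is 100. Not met.
- Low diastolic row needs < 50 mmHg; the lowest value is 58. Not met.
- Heart-rate rows need > 120 or < 50 bpm; the values are 70 to 85. Not met.

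The event appears nowhere in the PCR vital-signs table.

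**Step 3: size.** The documents give neither the frequency of postural falls nor the distribution of pulse response, so no under-count can be derived. To show how wide the possibilities are, assume that heart-rate rise among subjects with a qualifying systolic fall is normal with mean m of 5 to 20 bpm and SD s of 8 to 12 bpm. The share reaching 25 bpm is 1 − Φ((25 − m)/s):

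- m = 5, s = 8: 1 − Φ(2.5) = 0.006
- m = 20, s = 12: 1 − Φ(0.417) = 0.338

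Under these assumptions about 66% to 99% of such falls would go unflagged. The inputs have no source in the documents, so this is an illustration and not an estimate.

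**The case against.** The strongest reply is that an eligibility rule and a PCR flag do different jobs. These documents set them apart elsewhere: diastolic pressure above 95 mmHg for exclusion against above 105 for the flag, AST or ALT above 2 against at least 3 times the upper limit of normal, hemoglobin at most 9 g/dL against 11.5 (men) or 9.5 (women). Protocol Section 3.8.3.2 also says that meeting an exclusion criterion after randomization calls for individual assessment, not automatic discontinuation. This stands: a difference in thresholds is not in itself an error, and the entry rule is not automatically the standard for counting safety events. But those pairs apply different cut-offs to the same measurement, so a large enough departure reaches the flag. Here a second measurement is made compulsory and a limb is absent. No reason is given; the footnote citing a regulatory draft is attached to the heart-rate, systolic and diastolic rows, not to the orthostatic one.

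A reader might infer that the missed falls are lost altogether. The documents do not support that. The investigator may report an adverse event, a low absolute reading can enter the systolic or diastolic row, and mean changes are tabulated. None of these counts postural falls systematically.

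A reader might also infer that the SAP departs from the protocol, or that the flag is stricter throughout. Neither is so: the two appendices agree, and the flag accepts a smaller systolic fall and a sitting reading.

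The list of summary tables (SAP Section 12, updated in Addendum 2) was not in the text available, so a further table cannot be ruled out. The text that can be read specifies none.

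**Conclusion.** The concern holds as a gap in one descriptive safety count. The orthostatic row misses any pressure fall without a 25 bpm rise and any isolated diastolic fall, including falls that meet the trial's own exclusion definition. Other capture is unsystematic. This follows from the wording of the two rules and needs no numerical assumption.

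The size of the under-count is unknown. It would be tempting to conclude that a drug effect is being hidden or that the comparison between arms is biased. The documents do not support this: they report no orthostatic incidence, and if the flag caught the same share of events in both arms it would lower both counts and leave their expected ratio unchanged. What is lost is events, and with them the ability to see a difference.

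No hypothesis test is planned on this row, and the primary and key secondary analyses are untouched. The change is worth making because it is cheap and serves the secondary objective. Which definition is clinically right is not judged here.

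**What to change.** Keep the current flag and its row. Add to SAP Section 9.3 one supplementary incidence table by treatment group using the pressure limbs already in criterion 11: systolic fall of at least 30 mmHg or diastolic fall of at least 20 mmHg, supine to standing, within 3 minutes, not present at baseline. Report symptomatic cases alongside where symptoms were recorded.

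Show by arm the number of visits with supine, sitting and standing readings. SAP Section 8.1.1 acknowledges occasional virtual visits, at which these may be missing; it says that the screening, Day 1 and end-of-trial visits were required in person.

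State in the SAP why the appendix and exclusion definitions differ, or reconcile them. Also say how a row that disregards baseline status fits a table described as treatment-emergent.

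The cost is one descriptive table from readings already scheduled at every treatment visit, plus a sentence or two of explanation. No new data collection is needed and no rule for managing subjects changes.
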